5.4.2 Adaptive Trial Definitions

Clinically Significant Difference (CSD): The CSD used in the adaptive model relative to the change from baseline over time for placebo in the derived ADCOMS. The CSD for this study represents an approximate 25% reduction compared to placebo in the progression of AD as measured by the derived ADCOMS.

Maximum Effective Dose (d_{Max}): The dose that achieves the greatest treatment effect.

ED₉₀: The ‘simplest’ dose regimen that achieves at least 90% of the d_{Max} treatment effect. The term ‘simplest’ reflects the preference for dosing frequency and amount when considering the treatment arms for the study and while taking efficacy into account (monthly administration is preferred over bi-weekly administration and lower doses are preferred over higher doses, with priority placed on frequency of administration). Thus, the rank order of prioritized doses (beginning with the simplest) is: 5 mg/kg Q4wk, 10 mg/kg Q4wk, 2.5 mg/kg Q2wk, 5 mg/kg Q2wk, and 10 mg/kg Q2wk.

Early Success: The study meets early success criteria if the probability that the ED₉₀ at 12 months of treatment is better than the placebo by the CSD is at least 0.95. Early success is achieved before all subjects complete 12 months of treatment and can only be determined once ≥ 350 subjects are randomized. If early success is declared prior to full randomization, the randomization of new subjects will stop. Subjects already randomized into the study will receive 18 months of treatment.

Futility: The study meets statistical futility criteria if the probability that the ED₉₀ is better than the placebo by the CSD is less than 0.05 (with ≤ 300 subjects randomized) or 0.075 (with ≥ 350 subjects randomized) at 12 months of treatment. If the study meets statistical futility criteria, the sponsor will make the final decision pertaining to study futility after reviewing recommendations by the DSMB. Based on Sponsor's final decision, if the study continues to randomize subjects, it will be considered a failed study.

Study Success: The study will be considered a success if either of the following criteria are met for the 12 month treatment endpoint:

1. The study meets early success criteria (as outlined above)
2. The study reaches complete randomization and the Bayesian analysis at completion of 12 months of treatment results in an ED₉₀ with at least an 80% probability of being better than the placebo by the CSD

Further details are presented in the Simulation Plan, see [Appendix 13.2](#).

5.4.2.1 Dose-Response Model

The dose-response of the primary endpoint is modeled with a two-dimensional first-order normal dynamic linear model (NDLM), where Normal and inverse-Gamma priors are used. The primary efficacy analysis will calculate the Bayesian posterior probability (the conditional probability

when taking the observed data and prior efficacy information into account) that the dose identified as the most likely ED₉₀ achieves the CSD compared to the placebo arm. The probability is obtained using the Markov Chain Monte Carlo technique and the posterior distributions of the parameters in the dose response model. The posterior distribution is the distribution of parameter conditional on the data observed from the study. A detailed description of the NDLM and simulations is provided in the Simulation Plan, [Appendix 13.2](#) of this document.

5.4.2.2 Longitudinal Model

At each interim analysis there will be subjects who have complete or incomplete information. Some subjects will have complete information up to and including 12 months. Other subjects will have earlier observations, but no 12-month observations. There will be subjects with no observations.

The information from subjects with incomplete observations is utilized to the extent that the earlier values are correlated to the final 12-month value. A Bayesian model is built to learn from the accruing information on the association between the early values, and the final endpoint at 12 months. Further details on the longitudinal model are presented in the Simulation Plan, see [Appendix 13.2](#).

5.4.3 Report of Bayesian Analysis of Primary Endpoint in Adaptive Trial

The Bayesian analysis of primary endpoint as described in [Section 5.4.1](#) will be performed by an independent data analysis group (Tessella) and the analysis results will be reported in a separate document, IMC (Interim Monitoring Committee) report, at time of success at IA and the Bayesian analysis at 12 months. The following analysis outputs will be provided in this report:

1. Area chart plot of number of subjects randomized over time by treatment group.
2. Scatter plot of primary endpoint along with NDLM estimate of mean \pm 2 SD by treatment group. Each subject will be plotted with marker type and color identifying the last visit in case some subjects do not have 12 months visit.
3. Summary of posterior estimate of mean and standard deviation of primary endpoint for each treatment group.
4. Plot of NDLM estimates of primary endpoint (mean \pm 2 SD) showing Bayesian dose-response relationship based on the two-dimensional first-order NDLM.
5. Summary of posterior probabilities of being dMax and ED₉₀, superiority to placebo, and superiority to placebo by CSD for each dose.
6. Column chart plot of Bayesian posterior probabilities as number 5 above for each dose.

5.4.4 Secondary Efficacy Analyses

The Full Analysis Set will be used in secondary efficacy analyses.

Key Secondary Endpoint Analyses

Key Secondary endpoints and corresponding analyses are ordered to reflect the most recent FDA draft guidance (February, 2018) and EMA Final Guideline (February, 2018) that prioritize effects on pathophysiology in early AD, as measured by biomarkers. Conventional analysis will be performed using all available data at the time of success (if applicable), and at 18 months of treatment, regardless of success. As described in section 5.4.1.2, conventional analysis will be based on the MMRM model including baseline as covariate, with treatment group, visit, randomization stratification variables (i.e., clinical subgroup [MCI due to AD, Mild Alzheimer's Disease Dementia], the presence or absence of ongoing AD treatment [AChEIs or memantine or both], *APOE4* status [positive, negative]), region, treatment group-by-visit interaction as fixed effects. If there is an imbalance across treatment groups based on randomization stratification variables, additional MMRM model will be run without the randomization stratification variables. In addition, ANCOVA model will also be used with treatment as a factor and baseline value as a covariate. These statistical models will be used to compare the combined 10 mg dose group (including bi-weekly and monthly regimens) with placebo for the key secondary endpoints. The rationale for combining the two 10 mg dose regimens is to account for the loss of subjects positive for *APOE4* in the 10 mg/kg biweekly dose group and the inability to randomize *APOE4* carriers to the 10 mg/kg biweekly group following a regulatory request by European Health Authorities in July 2014.

In addition, analysis will be performed for the following treatment comparisons:

- Combining 2 high doses (10 mg bi-weekly + 10 mg monthly), 2 middle doses (5 mg bi-weekly + 5 mg monthly), and the 2.5 mg bi-weekly dose, resulting in 3 treatment comparisons with placebo (for dose response)
- ED₉₀ dose of BAN2401 versus placebo, where the ED₉₀ dose of BAN2401 will be established by Bayesian analysis at 18 months as described in the next paragraph
- By treatment regimen (10 mg bi-weekly, 10 mg monthly, 5 mg bi-weekly, 5 mg monthly, 2.5 mg bi-weekly, placebo)
- Combining the top 3 doses (10 mg bi-weekly, 10 mg monthly, and 5 mg bi-weekly) versus placebo

The key Secondary endpoints (ADCOMS, CDR-SB, and ADAS-Cog) will also be analyzed separately within subjects with MCI and mild AD dementia.

Change from baseline in the ADCOMS at 18 months will be analyzed, as a sensitivity analysis to the conventional analysis, using the same Bayesian methodology as that for analysis of change from baseline in the ADCOMS at 12 months, but using the full 18 months of efficacy data with the model projecting to 18 months of treatment. The Bayesian analysis of change from baseline in the ADCOMS at 18 months is positive if the analysis results in an ED₉₀ dose with at least an 80% probability of being better than the placebo by the CSD. The ED₉₀ dose will be identified based on change from baseline in the ADCOMS at the 18 month Bayesian analysis and will be used to compare ED₉₀ dose of BAN2401 and placebo in the above sensitivity analyses for all key secondary endpoint analyses.

Specifically, the following Bayesian analyses will be performed at 18 months:

- Fit the 2-dimensional NDLM Bayesian model defined in [Appendix 13.2](#) with 5 doses across 2 schedules of administration for the 18-month endpoint. This includes imputation of missing values from the longitudinal model.
- Compare placebo versus the combined 10mg dose group. This includes imputation of missing values from the longitudinal model.
- Fit a one-dimensional Bayesian model with 3 doses: 2.5mg dose group, combined 10mg dose group, and combined 5mg dose group. This will be a one-dimensional NDLM model with imputation of missing values from the longitudinal model.
- Fit the European Prevention of Alzheimer’s Dementia (EPAD) disease progression model for selected doses versus the placebo control.

In this study, subjects consented to PET sub-study have been using two different tracers for PET scan: Florbetapir and Flutemetamol. Only less than 10 subjects have used Flutemetamol and the rest have used Florbetapir. It is possible that different tracers may yield different results and data using different tracers may not be directly comparable, therefore only subjects using Florbetapir will be included in summary tables and other statistical analysis based on PET data. Subjects using Flutemetamol will only be listed and will not be included in summary tables or other statistical analysis based on PET data.

Other Secondary Endpoint Analyses

The same analysis described above for key secondary endpoints will be performed for other secondary endpoints.

For vMRI and amyloid PET endpoints, the adjusted p-value based on Dunnett-Hsu method with 1-sided alpha of 0.05 will also be provided in addition to the p-value corresponding to pairwise comparison.

5.4.5 Other Efficacy Analyses

No other efficacy analyses are planned for this study.

5.5 Pharmacokinetic, Pharmacodynamic, and PHARMACOGENOMIC/PHARMACOGENETIC ANALYSES

Further details for the analyses described below will be presented in a separate analysis plan.

5.5.1 Pharmacokinetic Analyses

The Safety Analysis Set will be used for individual BAN2401 serum and CSF concentration listings. The PK Analysis Set will be used for summaries of BAN2401 serum and CSF concentrations.

A population PK approach will be used to characterize the PK of BAN2401. The effect of covariates (i.e., demographics) on BAN2401 PK will be evaluated. The PK model will be parameterized for clearance (CL) and volumes of distribution. Derived exposure parameters such

as AUC will be calculated from the model using the individual posterior estimate of CL and dosing history.

5.5.2 Pharmacodynamic Analyses

The PD Analysis Set will be used for the summaries and analyses of CSF biomarkers. CSF A β (1-42), t-tau, and p-tau will be assessed and data presented graphically. Baseline levels and changes in t-tau and p-tau will be correlated with changes in CSF A β (1-42), imaging markers, and *APOE4* status. Summary statistics for CSF biomarkers will be assessed for evidence of a dose relationship.

5.5.3 Pharmacokinetic/Pharmacodynamic

The PK/PD relationship between CSF biomarker levels and serum PK parameters or CSF concentrations of BAN2401 will be explored graphically, and any emergent relationship will be explored through population PK/PD modeling. These serum PK parameters include SS, C_{max} and AUC_(0-t) derived from the population PK model. The PK/PD relationship between serum PK parameters and CSF concentrations of BAN2401 with other biomarkers may also be explored using similar methods.

Additionally, the relationship between various serum PK parameters (e.g. C_{max}) or CSF concentrations of BAN2401 and the derived ADCOMS at 12 months, and the relationship between various PK exposure parameters or CSF concentrations of BAN2401 and the change from Baseline for 12 and 18 months in Modified ADAS-cog, CDR-SB and MMSE, will be explored graphically. Any emergent relationships will be explored through population PK/PD modeling.

The relationship between exposure to BAN2401 and most frequent AEs will also be explored.

5.5.4 Pharmacogenomic/Pharmacogenetic Analyses

APOE4 genotypes will be used in the statistical analysis to determine the effects on treatment response and safety.

Exploratory pharmacogenomics and biomarker analyses may be performed and reported separately. Details of these analyses may be described in a separate analysis plan.

5.6 SAFETY ANALYSES

Evaluations of safety will be performed on the Safety Analysis Set. The incidence of AEs (including changes from baseline in physical examination), out-of-normal-range laboratory safety test variables, abnormal ECG findings, anti-BAN2401 antibody titers, and out-of-range vital signs, suicidality (C-SSRS), along with change from baseline in laboratory safety test variables, ECGs, safety MRI, and vital sign measurements, will be summarized by treatment group using descriptive statistics. The safety analysis will be also be summarized by the following safety subgroups: age (≤ 65 , $65 < \text{age} < 80$, ≥ 80 years), sex (male, female), race (white, black, Asian, other), region, *APOE4* status, and clinical subgroup (MCI due to AD – intermediate likelihood or mild Alzheimer’s disease dementia).

Study Day 1 for all safety analyses is defined as the date of the first dose of study drug.

5.6.1 Extent of Exposure

Extent of exposure to study drug will be summarized as cumulative extent of exposure from Day 1 to Week 6 initially, and at 3 months increments thereafter. The cumulative number and percent of subjects will be presented by treatment group. Duration of exposure will be summarized using descriptive statistics and by duration categories; Day 1 to 6 weeks, 6 weeks to 3 months, and 3-month intervals thereafter. The number and percent of subjects will be presented by each duration category and treatment group. Overall exposure (number of subject-months) is defined as summation over all subjects' exposure durations and will be summarized by treatment group.

5.6.2 Adverse Events

The AE verbatim descriptions (investigator terms from the CRF) will be classified into standardized medical terminology using the Medical Dictionary for Regulatory Activities (MedDRA). Adverse events will be coded to the MedDRA (Version 15.0 or higher) lower level term (LLT) closest to the verbatim term. The linked MedDRA preferred term (PT) and primary system organ class (SOC) will also be captured in the database.

A treatment-emergent AE (TEAE) is defined as an AE that emerged during treatment or within 90 days following the last dose of study drug, having been absent at pretreatment (Baseline) or

- Reemerged during treatment, having been present at pretreatment (Baseline) but stopped before treatment, or
- Worsened in severity during treatment relative to the pretreatment state, when the AE was continuous.

TEAEs and AEs will be followed for the entire duration of the study. Only those AEs that are treatment emergent will be included in summary tables. All AEs, treatment emergent or otherwise, will be presented in subject data listings.

Treatment-emergent AEs (TEAEs) will be summarized by treatment group on the Safety Analysis Set. The incidence of TEAEs will be reported as the number (percentage) of subjects with TEAEs by SOC and PT. A subject will be counted only once within a SOC and PT, even if the subject experienced more than one TEAE within a specific SOC and PT. The number (percentage) of subjects with TEAEs will also be summarized by maximum severity (mild, moderate, or severe). The number (percentage) of subjects with TEAEs will also be summarized by relationship to study drug (possibly related, probably related, and not related). TEAEs of special interest will be summarized similarly.

Adverse events will be summarized by the following subgroups: age (≤ 65 years, $65 < \text{age} < 80$, ≥ 80 years), sex (male, female), race (white, black, Asian, other), region, clinical subgroup (MCI due to AD – intermediate likelihood and mild Alzheimer's disease dementia), presence or absence of ongoing AD treatment (i.e., AChEIs and/or memantine), and *APOE $\epsilon 4$ carrier status* (positive, negative).

The number (percentage) of subjects with TEAEs leading to death will be summarized by MedDRA SOC and PT for each treatment group. A subject data listing of all AEs leading to death will be provided.

The number (percentage) of subjects with treatment-emergent serious adverse events (SAEs) was summarized by MedDRA SOC and PT for each treatment. A subject data listing of all SAEs was provided.

The number (percentage) of subjects with TEAEs leading to discontinuation from study drug will be summarized by MedDRA SOC and PT for each treatment. A subject data listing of all AEs leading to discontinuation from study drug will be provided.

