5.6.4 ANTI-DRUG (BAN2401) ANTIBODIES (ADA)

Definitions for BAN2401 Treatment Arms

ADA analysis for BAN2401 treatment arms will be based on evaluable subjects, which is defined as subjects who were treated with BAN2401 and had at least one valid post treatment ADA sample. ADA positive subjects are defined as those subjects with a treatment-induced or treatment-boosted ADA response, where treatment-induced response means ADA developed following drug administration, and treatment-boosted response means ADA already existed before treatment and boosted to a higher titer following drug administration. ADA negative subjects are those without a treatment-induced or treatment-boosted ADA response. It is possible in some instances that some subjects who did not have a measured positive ADA response during the treatment period (i.e., were negative for ADA) may not be confirmed negative due to drug interference in the sample testing process. Those subjects will be classified as ADA negative*. This distinction will be reserved only for those subjects who had PK level \geq drug tolerance limit of the assay and did not have positive ADA samples at any visits, and did not have ADA samples collected at the 3-month follow up visit. If a subject had a negative sample at the 3-month follow up visit and negative samples at all previous visits, then the subject is considered to be confirmed ADA negative. ADA incidence rate is defined as the proportion of ADA positive subjects among all ADA evaluable subjects.

Definitions for Placebo Treatment Arm

For placebo arm, subjects are unevaluable for an immune response to study drug treatment but will be evaluated for a baseline ADA response. Placebo subjects with a baseline ADA response are defined as those with at least one positive ADA sample at any visit.

ADA prevalence rate is defined as the proportion of subjects with baseline ADA response in placebo arm plus BAN2401 subjects with positive ADA samples prior to treatment among all treated subjects.

Analysis

ADA incidence rate and the maximum titer for ADA positive subjects will be summarized by treatment group. ADA prevalence rate will also be summarized.

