8.1 DEFINITION OF VISIT WINDOWS

The protocol specified visits/weeks and corresponding time windows used for visit-wise analyses are presented in terms of days relative to the first dose. For subjects that are randomized, the last available assessment on or before the date of the first dose of study drug will be used as the Baseline-Day 1.

Different assessment may have different visit schedule. A general rule for determining a time window for each scheduled visit is to split the two consecutive scheduled visits in the middle point of the two consecutive visits. For example, the time window for visit X is from the middle

point between visit (X-1) and X (exclusive) to the middle point between visit X and (X+1) (inclusive). According to protocol, “assessments should take place on the first day of the study visit in the designated study week except as noted below (footnotes h, i, and j pertaining to imaging assessments, and footnote o pertaining to CSF sample collection)” (see [page 96, Protocol Amendment 08](#)). Therefore, the scheduled day corresponding to scheduled visit at week Y is $((Y-1)*7+1)$ days. For example, the scheduled day for scheduled visit at weeks 1, 3, and 5 are Day 1, Day 15, and Day 29, respectively and the corresponding time window for scheduled visit at weeks 1 and 3 are [Day 1, Day 8] and [Day 9, Day 22], respectively

For scheduled every 3 months post baseline efficacy assessments, the analysis visits are the same as the scheduled visits. Any window rules will not apply. This is per ITT principle and also assumes that the actual assessment dates are independent from any other factors or are random and centered at scheduled time point.

For Early Termination (ET) visit and Follow Up (FU) visit, the following rules apply for efficacy assessment:

- If the last scheduled 3-month assessment before early termination (LS), ET assessment and FU assessment are in three separate sequential 3-month windows, e.g., Window(x), Window (x+1) and Window(x+2), then the analysis visits for last scheduled 3-month assessment (LS), ET assessment and FU assessment will be x, x+1 and x+2, respectively.
- If both LS and ET are in Window(x) and FU is in Window(x+1) [note: this is the most likely situation since ET and FU are expected to be separated by 3 months], then analysis visit is x for LS (per rule 1.) and (x+1) for FU and ET will not be included in Bayesian analyses and MMRM analyses.

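### The TEAE definition gives its 90-day post-dose window only to new events, so baseline conditions that recur or worsen after the last dose are left out of the AE summary tables

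*SAP*

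**What the plan says.** SAP Section 5.6.2 defines a TEAE through three alternatives:

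- **New events:** an AE that "emerged during treatment or within 90 days following the last dose of study drug, having been absent at pretreatment (Baseline").
- **Re-emerged events:** "Reemerged during treatment, having been present at pretreatment (Baseline) but stopped before treatment, or" the third alternative.
- **Worsened events:** "Worsened in severity during treatment relative to the pretreatment state, when the AE was continuous".

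The same section then ties the tables to this definition: "Only those AEs that are treatment emergent will be included in summary tables". The listings are wider: "All AEs, treatment emergent or otherwise, will be presented in subject data listings".

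The tables affected are those by system organ class and preferred term, by maximum severity and by relationship to study drug, and those for events of special interest, deaths, serious events and events leading to discontinuation of study drug.

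**The concern.** The post-dose period is open to one kind of event and closed to two others, and the SAP gives no reason for the difference. Suppose two subjects each have an AE 30 days after their last infusion. One has a headache never reported before; the other has a baseline headache that has become severe. The first is counted and the second is not. The same holds if the worsened condition is serious or fatal.

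Safety and tolerability is one of the two primary objectives (Section 3.1.1). The AE tables are where treatment groups are compared on adverse events. A worsened baseline condition that appears only in a listing enters no count by arm.

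**Working it through.** **1. Do the second and third limbs include the 90 days?** The SAP does not define *during treatment* for this purpose, so a generous reader could take it to cover the post-dose period. The first limb blocks that reading. It sets *during treatment* beside the 90 days after the last dose as two alternatives joined by *or*. If the first phrase already contained the second, the second would add nothing. The consistent reading is that the phrase excludes the post-dose window, so the other two limbs do not have it.

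**2. Could such events enter through the first limb?** No. That limb requires the AE to have been absent at baseline. The other two describe conditions present at pretreatment, either stopped before treatment or continuous.

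**3. What is lost?**

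| Event within 90 days after last dose | TEAE as written? | In AE summary tables? | In listings? |
|---|---|---|---|
| New, absent at baseline | Yes | Yes | Yes |
| Present at baseline, stopped, then re-emerged after last dose | No | No | Yes |
| Present at baseline, continuous, worsened after last dose | No | No | Yes |

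**4. How long is the excluded period?** The SAP gives no figure of its own to reproduce. Inputs:

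- 39 possible biweekly infusions over 18 months and 26 over 12 months (Section 5.2.6).
- Scheduled day for week Y = (Y − 1) × 7 + 1 (Section 8.1).
- Window of 90 days (Section 5.6.2).
- Assumption: treatment ends on the day of the last infusion.

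Infusion k of a biweekly schedule starting in week 1 falls in week 1 + 2(k − 1).

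- 39th infusion: week 1 + 2 × 38 = 77, so Day 76 × 7 + 1 = 533. The window ends on Day 533 + 90 = 623. Share closed to re-emerged and worsened events: 90/623 = 14.4%.
- 26th infusion: week 1 + 2 × 25 = 51, so Day 50 × 7 + 1 = 351. The window ends on Day 441. Share: 90/441 = 20.4%.
- One infusion only: Day 1, window to Day 91. Share: 90/91 = 98.9%.

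**5. Sensitivity to the assumption.** If treatment is instead taken to run through one 14-day dosing interval after the last infusion, 90 − 14 = 76 days stay closed. The shares become 76/623 = 12.2%, 76/441 = 17.2% and 76/91 = 83.5%. The period shortens but does not close, and the pattern by time of stopping is the same.

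**The case against.** The strongest reply is that no event is lost. All AEs are listed, and Sections 5.6.2 and 5.6.4 to 5.6.7, with the opening of Section 5.6, leave laboratory values, vital signs, ECGs, safety MRI and anti-drug antibodies to rules that do not use the TEAE definition. That stands. A reader might infer that these events vanish from all safety tables, and the document does not support that: the exclusion is confined to the AE summary tables. Listings, however, do not replace a count by arm.

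A second reply is that the percentages are shares of calendar days, depend on where treatment is taken to end, and are extreme only for subjects who stop very early. That also stands. They say nothing about how many events fall in the period, and the number may be small.

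A reader might also infer that the between-arm comparison is biased toward showing no harm. That would need discontinuation to differ between arms and baseline conditions to worsen after the last dose. The SAP has no figure for either, and new post-dose events are still counted for 90 days.

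Finally, a reader might infer that findings first made at the follow-up visit are lost as well. The SAP mentions subjects who "did not have ADA samples collected at the 3-month follow up visit", and says that "ET and FU are expected to be separated by 3 months", and three months can exceed 90 days. But this does not follow from the asymmetry. A new finding falls under the limb that does have the 90 days, and it turns on when the event emerged, not on when it was reported. Whether the visit falls beyond day 90 depends on timing that this SAP leaves to the protocol, and the statement on spacing stands in rules for efficacy assessments.

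**Conclusion.** The fault is in a stated rule and can be seen on its face. Under Section 5.6.2 as written, a baseline condition that re-emerges or worsens within 90 days after the last dose is excluded from all AE summary tables, although a new event on the same day is included.

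For a biweekly completer with the last infusion on Day 533, the exclusion covers 90 of 623 days (14%), provided treatment is taken to end at that infusion. The share rises the earlier a subject stops. The number of events affected cannot be derived from the document, and neither can any direction of bias between arms. This should be corrected because the inconsistency is plain and the remedy is cheap, not because a distortion has been shown.

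**What to change.** Replace the definition in Section 5.6.2 with one that applies a single fixed window to all three limbs: a TEAE is an AE that emerges, re-emerges, or worsens in severity relative to the pretreatment state, from the first dose to 90 days after the last dose of study drug. The definition then no longer depends on the undefined phrase *during treatment*.

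The window should stay fixed. Stretching it to the actual follow-up visit would give subjects unequal risk periods according to attendance.

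The cost is one sentence in the SAP and one derivation flag. No new data are needed, since the section already lists every AE. The downside is that TEAE counts may rise slightly.
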